6.5.3 Supportive Care

Treatment guidelines for participants who experience drug-related AEs are provided in Section 6.6.

Participants should receive appropriate supportive care measures, as deemed necessary by the treating investigator including, but not limited to, the items outlined below:

- Nausea/vomiting: Nausea and vomiting should be treated aggressively, and consideration should be given in subsequent cycles to the administration of prophylactic antiemetic

therapy according to standard institutional practice. Participants should be strongly encouraged to maintain liberal oral fluid intake.

- Anemia: Transfusions and/or erythropoietin may be utilized as clinically indicated for the treatment of anemia but should be clearly noted as concomitant medications.
- Neutropenia: Prophylactic use of colony-stimulating factors including G-CSF, pegylated G-CSF, or GM-CSF is not allowed in this study. Therapeutic use of G-CSF is allowed in participants with Grade 3-4 febrile neutropenia.
- Thrombocytopenia: Transfusion of platelets may be used if clinically indicated. ITP should be ruled out before initiation of platelet transfusion.
- Anti-infectives: Participants with a documented infectious complication should receive oral or IV antibiotics or other anti-infective agents, as considered appropriate by the treating investigator for a given infectious condition, according to standard institutional practice.

Treatment by local surgery and/or radiation therapy of isolated or symptomatic progressing lesions in the setting of improving baseline disease may be permitted for palliative or potentially curative management. Subsequently, all interventions, including continuation of study intervention, should be discussed with the Sponsor Clinical Director or designee.

6.6 Dose Modification (Escalation/Titration/Other)

6.6.1 Dose Modification due to Adverse Events

AEs (both nonserious and serious) associated with MK-1454 and/or pembrolizumab exposure may represent an immunologic etiology. These AEs may occur shortly after the first dose or several months after the last dose of treatment.

The CTCAE Version 5.0 must be used to grade the severity of AEs. The investigator may attribute each toxicity event to MK-1454 alone, to pembrolizumab alone, or to the combination, and modify the dose according to [Table 5](#), [Table 6](#), and [Table 7](#). If a dose modification for toxicity occurs with MK-1454, the dose may not be re-escalated to the dose that preceded the dose modification. If 1 (or more) treatment is held for toxicity, the schedule for restarting the agents should correspond with the next treatment cycle once the toxicity is resolved.

Holding of 1 treatment and not the other treatment is appropriate if, in the opinion of the investigator, the toxicity is clearly related to one of the study interventions. For example, in the combination arm (Arm 1), if MK-1454 is held due to an AE attributed to it, then pembrolizumab may continue to be administered. Appropriate documentation is required with regard to which treatment the investigator is attributing the AE. If, in the opinion of the investigator, the toxicity is related to the combination of 2 treatments, then both treatments should be held according to recommended dose modifications.

Participants may have only 1 dose modification of MK-1454 throughout the course of the study. If further toxicity occurs or the criteria for resuming treatment are not met, the participant must be discontinued from MK-1454. If a participant experiences several toxicities and there are conflicting recommendations, follow the most conservative recommendation.

Exceptional circumstances to following the dose modification tables below may be considered after consultation with the Sponsor.

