6.6.1.1 Dose Modification for MK-1454

Guidelines for dose modification and/or treatment discontinuation for drug-related injection site reactions and for CRS AEs are provided in [Table 5](#) and [Table 6](#), respectively.

The investigator should first assess an AE to determine the CTCAE Version 5.0 severity grade. For AEs that are \leq Grade 2, the decision to hold treatment is per medical assessment by the investigator. Once the AE has resolved to Grade 0 or 1, treatment with MK-1454 can be restarted. If the AE persists, discuss with the Sponsor with regard to selecting a different injection site or discontinuation. MK-1454 should be discontinued permanently following a severe or life-threatening AE.

In case toxicity does not resolve to Grade 0-1 within 12 weeks after last intervention, MK-1454 should be discontinued after consultation with the Sponsor.

With investigator and Sponsor agreement, participants with a laboratory AE still at Grade 2 after 12 weeks may continue intervention in the study only if asymptomatic and controlled.

After any Grade 4 drug-related AE, participants should not restart study intervention without consultation with the Sponsor (Toxicity must have resolved to Grade 0-1 or baseline prior to restarting).

Pembrolizumab treatment will be modified for the AEs described in Section 6.6.1.4.

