6.6.1.1.1 Guidelines for Management of Intratumoral Injection Site Reactions

Guidelines for management of injection site reaction from intratumoral injection of MK-1454 are detailed in [Table 5](#).

Table 5 Intratumoral Injection Site Reaction Management Guidelines

NCI CTCAE Grade	MK-1454 Dose Modification	Treatment
Grade 1 Tenderness with or without associated symptoms (eg, warmth, erythema, itching)	No dose reduction warranted.	Observe. Dose to be held per medical assessment of the investigator. Analgesia as needed.
Grade 2 Pain; lipodystrophy; edema; phlebitis	Per medical assessment of the investigator: 
 Consider holding dose until resolution to Grade 1 or baseline. Consider decreasing dose of IT MK-1454 to [REDACTED] and limit injections to a maximum of 2 lesions per study visit. If AE persists, discuss continuation with Sponsor. 	Observe. Local care to injection site. Analgesia as needed. Consider injection into a different lesion, if available.
Grade 3 Ulceration or necrosis; severe tissue damage; operative intervention indicated	
 Hold dose until resolution to Grade 1 or Baseline. Decrease dose of IT MK-1454 to [REDACTED] and limit injections to a maximum of 2 lesions per study visit. If AE persists, discuss continuation with Sponsor. 	Wound care with consultation from institutional wound care specialist. Analgesia as needed. Consider injection into a different lesion, if available.
Grade 4 Life-threatening consequences; urgent intervention indicated	
 Permanently discontinue IT MK-1454 treatment. 	Aggressive wound care with surgical consultation. Analgesia as needed.

AE adverse events; CTCAE Common Terminology Criteria for Adverse Events (Version 5.0); IT intratumoral; NCI National Cancer Institute.

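### Section 6.6.1 makes stopping MK-1454 mandatory when the criteria for resuming are not met, but Section 6.6.1.1 and Tables 5 and 6 send the same case to discussion with the sponsor

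*Combined protocol and SAP*

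**What the plan says.** Section 6.6.1 sets the general rule. It caps changes to the experimental drug: "Participants may have only 1 dose modification of MK-1454 throughout the course of the study". The next sentence is: "If further toxicity occurs or the criteria for resuming treatment are not met, the participant must be discontinued from MK-1454". Two general clauses follow: "If a participant experiences several toxicities and there are conflicting recommendations, follow the most conservative recommendation", and "Exceptional circumstances to following the dose modification tables below may be considered after consultation with the Sponsor".

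Section 6.6.1.1 covers MK-1454 specifically:
- At Grade 2 or below, "the decision to hold treatment is per medical assessment by the investigator", and treatment can restart at Grade 0 or 1.
- For an event that does not settle: "If the AE persists, discuss with the Sponsor with regard to selecting a different injection site or discontinuation".
- After a severe or life-threatening event, MK-1454 should be stopped permanently.
- If toxicity has not reached Grade 0 or 1 within 12 weeks, MK-1454 should be stopped after consultation with the sponsor.
- A laboratory event still at Grade 2 after 12 weeks may continue on treatment if the investigator and sponsor agree and it is controlled and without symptoms.

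Tables 5 (injection site reactions) and 6 (cytokine release syndrome) give instructions by grade. At Grade 1 both say "No dose reduction warranted". At Grade 2 holding and reducing are to be considered; at Grade 3 both are directed. In both tables the dose-modification entries for Grades 2 and 3 end with "If AE persists, discuss continuation with Sponsor".

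Appendix 3 (Section 10.3.4) describes Grade 3 as severe or medically significant, and Grade 4 as life-threatening.

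**The concern.** A site treating a participant whose Grade 2 or Grade 3 event has not settled finds a duty to stop in one paragraph and an invitation to discuss continuing in others. Section 7.1 adds weight to the question: a toxicity that Section 6.6 specifies as a reason for permanent discontinuation is a mandatory reason to stop. Which sentence of Section 6.6 governs therefore also decides what counts as a protocol deviation.

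MK-1454 is what separates the two arms, the trial is open-label, and only Arm 1 is affected. Discontinuing study intervention because of an adverse event is a secondary endpoint. If sites follow different sentences, MK-1454 exposure and that endpoint will partly reflect how the text was read. There is also a safety side, since these are the instructions for an unresolved reaction to the experimental drug.

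**Working it through.** No arithmetic applies. The check is a comparison of the passages.

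**Step 1: the criterion for resuming.** Section 6.6.1 refers to such criteria without defining them. Section 6.6.1.1 gives Grade 0 or 1 for restarting; Tables 5 and 6 give Grade 1 or baseline for ending a hold. An event that stays above that level has not met the criterion.

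**Step 2: what each passage requires for that event.**

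| Place | Instruction | Force | Time frame |
|---|---|---|---|
| 6.6.1 | Discontinue MK-1454 | Mandatory | None stated |
| Tables 5 and 6, Grades 2 and 3 | Discuss continuation with the sponsor | By discussion | None stated |
| 6.6.1.1, event persists | Discuss another injection site or discontinuation | By discussion | None stated |
| 6.6.1.1, not at Grade 0 or 1 | Discontinue after consultation | Should | 12 weeks |
| 6.6.1.1, laboratory event still Grade 2 | May continue by agreement | Permissive | After 12 weeks |

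The first row conflicts with the second, third and fifth, and differs from the fourth in force and time frame.

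**Step 3: do the tables concern a participant already modified once?** At Grade 3 the bullet on discussing continuation follows the bullet directing a dose decrease, so it reaches such a participant. The conflict therefore survives even if the mandatory sentence in 6.6.1 applies only after the one modification. At Grade 2 the decrease is optional, so the participant may or may not have been modified.

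**Step 4: does another clause settle it?** The most-conservative clause applies when a participant has several toxicities with conflicting recommendations, not when text and table disagree about one toxicity. The exceptions clause permits departures from the tables; it does not address the mandatory sentence.

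**Step 5: Grade 3.** Section 6.6.1.1 calls for permanent discontinuation after a severe event, and Appendix 3 attaches that word to Grade 3. Tables 5 and 6 direct a hold and a reduced dose at Grade 3, and Table 6 describes a restart with sponsor approval. Here 6.6.1.1 disagrees with the tables, so the problem is not simply 6.6.1 against everything else.

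**Step 6: two undefined terms.** Further toxicity in 6.6.1 carries no grade. It may mean any toxicity, or only toxicity that would need a second modification. It is also not explicit whether a hold without a decrease counts as the one modification: holds sit under the column headed as MK-1454 dose modification in both tables, but the sentence in 6.6.1 barring re-escalation fits only a decrease, and holds have a sentence of their own.

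**The case against.** The passages can be read as a sequence: hold, discuss while the event persists, stop if it is unresolved at 12 weeks. Section 7.1 fits this, since it requires discontinuation after more than 12 consecutive weeks of interruption. Discussing continuation is not an instruction to continue, 6.6.1.1 names discontinuation as a possible outcome, and routing persistent events to the sponsor is a central check on differences between sites.

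Much of this is fair, and it narrows the conflict. It does not remove it. Section 6.6.1 sets no time frame and does not present itself as the last step of a sequence. Section 6.6.1.1 still softens the 12-week step to should, after consultation, and allows one class of unresolved event to continue beyond it. Sponsor discussion cannot align sites that stop under 6.6.1 without raising the case.

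Three stronger readings are tempting but not supported:
- A reader might infer that any Grade 1 tenderness after one modification forces a permanent stop. The trigger directly follows the cap on modifications and may mean toxicity needing a second one. Grade 1 warrants no reduction, so on that reading it triggers nothing. This is an ambiguity, not a proven contradiction.
- A reader might infer that one optional hold exhausts the allowance. The no-re-escalation sentence points the other way.
- A reader might infer a measurable distortion of the response-rate comparison, or attach a probability of forced stopping. The public text gives no per-injection toxicity rates, so a probability would rest on invented risks, and nothing in the documents yields an effect on the response rate.

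**Conclusion.** The concern holds in a limited form. For an adverse event that does not meet the criteria for resuming, 6.6.1 requires discontinuation of MK-1454, while 6.6.1.1 and the Grade 2 and Grade 3 rows of Tables 5 and 6 leave the matter to discussion, and no clause says which prevails. A related conflict exists at Grade 3 between 6.6.1.1 and the two tables. The meaning of further toxicity and the status of a hold are secondary ambiguities.

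The consequence is inconsistent stopping of MK-1454 between sites in Arm 1, bearing on participant safety, exposure and the secondary endpoint of discontinuation due to an adverse event. Its size cannot be quantified from the documents. The conclusion rests on two inferences: that the undefined criteria in 6.6.1 are those given in 6.6.1.1 and the tables, and that severe in 6.6.1.1 has the meaning Appendix 3 gives it.

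**What to change.** Reconcile 6.6.1, 6.6.1.1 and Tables 5 and 6:
1. Give each situation (event not resolved to the level for resuming, further toxicity after a modification, Grade 3 event) one obligation, mandatory or by discussion, and one time frame.
2. State what further toxicity means, including any grade limit.
3. State whether a hold without a dose decrease counts as the one permitted modification.
4. Say which text prevails if the body and a table differ on a single toxicity.

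Which rule stands is the sponsor's clinical decision; this point asks only that the passages agree. The cost is a few sentences in two sections and edits to two tables, with no new procedures or data.

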6.6.1.1 Dose Modification for MK-1454

Guidelines for dose modification and/or treatment discontinuation for drug-related injection site reactions and for CRS AEs are provided in [Table 5](#) and [Table 6](#), respectively.

The investigator should first assess an AE to determine the CTCAE Version 5.0 severity grade. For AEs that are \leq Grade 2, the decision to hold treatment is per medical assessment by the investigator. Once the AE has resolved to Grade 0 or 1, treatment with MK-1454 can be restarted. If the AE persists, discuss with the Sponsor with regard to selecting a different injection site or discontinuation. MK-1454 should be discontinued permanently following a severe or life-threatening AE.

In case toxicity does not resolve to Grade 0-1 within 12 weeks after last intervention, MK-1454 should be discontinued after consultation with the Sponsor.

With investigator and Sponsor agreement, participants with a laboratory AE still at Grade 2 after 12 weeks may continue intervention in the study only if asymptomatic and controlled.

After any Grade 4 drug-related AE, participants should not restart study intervention without consultation with the Sponsor (Toxicity must have resolved to Grade 0-1 or baseline prior to restarting).

Pembrolizumab treatment will be modified for the AEs described in Section 6.6.1.4.

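### For Grade 3 injection-site reactions and Grade 3 CRS, the text of Section 6.6.1.1 stops MK-1454 permanently while Tables 5 and 6 allow it to resume, and no precedence is stated

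*Combined protocol and SAP*

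**What the plan says.** Section 6.6.1.1 (Dose Modification for MK-1454) opens by sending two kinds of event to the tables: "Guidelines for dose modification and/or treatment discontinuation for drug-related injection site reactions and for CRS AEs are provided in" Tables 5 and 6. It then asks the investigator to assign a CTCAE grade, leaves holding to the investigator's judgement up to Grade 2, and continues: "MK-1454 should be discontinued permanently following a severe or life-threatening AE". No exception is made for injection-site reactions or CRS.

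The Grade 3 row of Table 5, whose descriptors are "Ulceration or necrosis; severe tissue damage; operative intervention indicated", says to hold the dose until the event improves to Grade 1 or baseline, lower the dose, limit the number of lesions injected, and talk to the Sponsor if the event persists. The Grade 3 row of Table 6 gives the same dose actions and adds that MK-1454 may be restarted once the Sponsor approves. Both tables keep permanent discontinuation for Grade 4.

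Three provisions of Section 6.6.1 bear on how to choose:

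- The rule for clashing advice: "If a participant experiences several toxicities and there are conflicting recommendations, follow the most conservative recommendation"
- The clause on departing from Tables 5 to 7: "Exceptional circumstances to following the dose modification tables below may be considered after consultation with the Sponsor"
- The cap on changes to the MK-1454 dose: "Participants may have only 1 dose modification of MK-1454 throughout the course of the study"

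Section 7.1 makes any related toxicity that Section 6.6 marks for permanent discontinuation a mandatory reason to stop study intervention.

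**The concern.** An investigator facing one Grade 3 injection-site reaction or one Grade 3 CRS event finds two incompatible instructions within the same part of the protocol. One site could re-expose the participant to MK-1454 and another could stop it for good, each with protocol text in support.

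The exposure is greatest for injection-site reactions. Table 5 calls for Sponsor discussion only if the reaction persists, so a Grade 3 reaction that resolves can lead to re-injection without any Sponsor contact under that table. Table 6 requires Sponsor approval before MK-1454 restarts after Grade 3 CRS.

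Discontinuation of study intervention due to an AE is a secondary endpoint. If sites resolve the conflict differently, part of the Arm 1 result on that endpoint will reflect how the rule was read rather than how the treatment was tolerated.

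**Working it through.** No formula applies; the check is a comparison of texts.

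**Step 1: does severe mean Grade 3 here?** Section 6.6.1 requires CTCAE Version 5.0 for grading severity. Section 10.3.4 labels Grade 3 as severe or medically significant and Grade 4 as life-threatening. The Section 6.6.1.1 paragraph is itself a ladder: grade the event, then a rule up to Grade 2, then the rule for severe or life-threatening events. If severe did not include Grade 3, that ladder would skip Grade 3. Table 5's Grade 3 row also uses the word: "Ulceration or necrosis; severe tissue damage; operative intervention indicated".

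**Step 2: text against tables, MK-1454 only.**

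| Event | Section 6.6.1.1 text | Table | Agree? |
|---|---|---|---|
| Grade 3 injection-site reaction | Permanent stop | Table 5: hold, reduce, may resume | No |
| Grade 3 CRS | Permanent stop | Table 6: hold, reduce, may restart with Sponsor approval | No |
| Grade 4 injection-site reaction | Permanent stop | Table 5: permanent stop | Yes |
| Grade 4 CRS | Permanent stop | Table 6: permanent stop | Yes |

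Count: 2 + 2 = 4 rows at Grade 3 or 4. The instruction differs in 2 of 4 and agrees in 2 of 4.

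**Step 3: does any rule settle it?** The most-conservative rule is conditioned on several toxicities, not on two instructions for one event; stretched to a single event, it would point away from the tables. The exceptional-circumstances clause governs departures from the tables but does not rank them against the text. Section 7.1 refers back to Section 6.6, so whether a Grade 3 event is a mandatory stop depends on which Section 6.6 text is applied.

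**Step 4: do other safeguards remove the risk?** Section 10.3.4 requires advance Sponsor approval of rechallenge when the event was serious and possibly caused by the product, or when re-exposure adds significant risk. The same section says that an event is not serious merely because it is rated severe, so not every Grade 3 reaction is caught. The limit of one MK-1454 dose modification takes effect only once the first modification has been used.

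**Related items, of lower standing.**

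- *Grade 4 restart.* Under the MK-1454 heading the protocol also says: "After any Grade 4 drug-related AE, participants should not restart study intervention without consultation with the Sponsor". If that covers MK-1454, it sits badly with the permanent stop. If it means pembrolizumab only, it does not; footnote d of Table 7 allows pembrolizumab to resume after some Grade 4 events. This is ambiguous, not an established conflict.
- *Agent in Table 6, Grade 4.* One column names MK-1454 and another names study intervention.
- *Interruptions over 12 weeks.* Section 6.4 asks for consultation and a documented joint decision when the cause is not drug-related or is administrative. Section 7.1 requires discontinuation after more than 12 consecutive weeks. It writes a Sponsor exception for radiographic progression but none for interruptions.
- *Cross-reference.* "Pembrolizumab treatment will be modified for the AEs described in Section 6.6.1.4" leads nowhere; the pembrolizumab rules are in Section 6.6.1.2. This is editorial.

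**The case against.** The best answer is that the specific governs the general. Section 6.6.1 tells the investigator to modify the dose by the tables and treats departures from them as exceptional. Section 6.6.1.1 opens by assigning both modification and discontinuation for these two event types to Tables 5 and 6. On that reading, the permanent-stop sentence covers other AEs only. Section 7.1's reference to the dose-modification guidelines could likewise mean the tables alone, which stop MK-1454 permanently only at Grade 4.

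This reading is plausible, and the text leans towards it. It is not written down. The paragraph containing the permanent-stop sentence speaks of AEs in general, and the sentence just before raises moving to another injection site if the event persists, which plainly reaches injection-site reactions. Text and tables therefore cover the same events and part company only at Grade 3.

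Some objections to the related items have force. The Grade 4 sentence is a restriction and does not direct a restart. In Table 6's Grade 3 row, the wording moves from study intervention to MK-1454 within the same cell, which suggests that the column uses the two interchangeably. Section 6.4 counts gaps for either agent, and one agent may be held while the other continues, so it can apply where Section 7.1 arguably does not; nor does it expressly permit resumption. These points support treating the items as clarifications rather than proven contradictions.

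It is also fair to say that divergent site behaviour is a foreseeable risk and has not been shown to occur.

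**Conclusion.** The concern holds. For a single Grade 3 injection-site reaction or Grade 3 CRS event, the text of Section 6.6.1.1 and the tables give MK-1454 instructions that cannot both be followed, and the protocol states no precedence. The conflict affects 2 of the 4 Grade 3 and Grade 4 rows, in Arm 1 only.

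The conclusion rests on reading severe as Grade 3, which Section 10.3.4 and the order of the Section 6.6.1.1 paragraph support. It does not depend on any redacted dose.

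No effect on the AE-discontinuation endpoint can be calculated, because the readable text gives no rate for these Grade 3 events. Alpha, power and the ORR analysis do not change. The matter should be fixed because it concerns re-exposure after a Grade 3 event and uniform conduct across sites.

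**What to change.** Reconcile the Section 6.6.1.1 sentence with the Grade 3 rows of Tables 5 and 6 so that each event and grade carries one instruction, or state which text prevails when two apply to a single event. The sponsor's clinical team decides which rule is intended; this review takes no position on it.

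In the same revision:

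- name the agent or agents covered by the Grade 4 restart sentence and by Table 6's Grade 4 row;
- reconcile Sections 6.4 and 7.1 on interruptions longer than 12 weeks;
- correct the reference to Section 6.6.1.4.

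The cost is wording only, by protocol amendment or clarification letter, with no extra participants or procedures.
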